**NOTES:**

- If the study treatment stop date is missing, then the AE will be considered to be On-Treatment.
- Time of study treatment dosing and start/stop time of AEs should be considered, if collected.

## 11.5. Appendix 5: Data Display Standards & Handling Conventions

### 11.5.1. Reporting Process

Software	

 
The currently supported versions of SAS software will be used.
 
	
Reporting Area	
HARP Server	UK1SALX00175
HARP Compound	One reporting effort will be set up for this study \ arenv \ arprod \ gsk2983559 \ mid205021 \final_01
Analysis Datasets	

 
Analysis datasets will be created according to Legacy Integrated Data Standards Library (IDSL) GSK A&R dataset standards
 
	
Generation of RTF Files	

 
RTF files will be generated for all tables within the final_01 reporting effort.
 
	

### 11.5.2. Reporting Standards

General

 
The current GSK Integrated Data Standards Library (IDSL) will be applied for reporting, unless otherwise stated (IDSL Standards Location: https://spope.gsk.com/sites/IDSLLibrary/SitePages/Home.aspx):             
 
4.03 to 4.23: General Principles
 
5.01 to 5.08: Principles Related to Data Listings
 
6.01 to 6.11: Principles Related to Summary Tables
 
7.01 to 7.13: Principles Related to Graphics
 
 
 
Do not include subject level listings in the main body of the GSK Clinical Study Report. All subject level listings should be located in the modular appendices as ICH or non-ICH listings
 
All data displays (Tables, Figures & Listings) will use the term "Subject" which reflects CDISC and GSK Data Display Standards terminology.
 

Formats

 
All data will be reported according to the actual treatment the participant received, unless otherwise stated.
 
GSK IDSL Statistical Principles (5.03 & 6.06.3) for decimal places (DP's) will be adopted for reporting of data based on the raw data collected, unless otherwise stated.
 
Numeric data will be reported at the precision collected on the eCRF.
 
The reported precision from non eCRF sources will follow the IDSL statistical principles but may be adjusted to a clinically interpretable number of DP's.
 

Planned and Actual Time

 
Reporting for tables, figures and formal statistical analyses:             
 
Planned time relative to dosing will be used in figures, summaries, statistical analyses and calculation of any derived parameters, unless otherwise stated.
 
The impact of any major deviation from the planned assessment times and/or scheduled visit days on the analyses and interpretation of the results will be assessed as appropriate.
 
 
 
Reporting for Data Listings:             
 
Planned and actual time relative to study drug dosing will be shown in listings (Refer to IDSL Statistical Principle 5.05.1).
 
Unscheduled or unplanned readings will be presented within the subject's listings.
 
 
 

Unscheduled Visits	

 
Unscheduled visits will not be included in summary tables and/or figures.
 
All unscheduled visits will be included in listings.
 
	
Descriptive Summary Statistics	
Continuous Data	Refer to IDSL Statistical Principle 6.06.1
Categorical Data	N, n, frequency, %
Graphical Displays	

 
Refer to IDSL Statistical Principals 7.01 to 7.13.
 
	

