### 5.2. Baseline Definitions

- For all endpoints (except as noted in baseline definitions) the baseline value will be the latest pre-dose assessment with a non-missing value, including those from unscheduled visits. If time is not collected, Day 1 assessments are assumed to be taken prior to first dose and used as baseline.
- For Part A, baseline definitions defined in the table are applicable to each treatment period.
- Unless otherwise stated, if baseline data is missing no derivation will be performed and baseline will be set to missing. The mean of triplicate measurements at any given time point will be used as the value for that time point unless otherwise stated.

Parameter	Study Assessments Considered as Baseline			Baseline Used in Data Display
	Screening	Day -1	Day 1 (Pre-Dose)	
Safety				
Clinical Chemistry/ Haematology/ Urinalysis	X	X	X	Day 1
12-lead ECG	X	X 	X 	Day 1
Vital Signs	X	X	X 	Day 1
Pharmacokinetic				
PK Concentrations			X	Day 1
Pharmacodynamic				
PD Blood sample			X	Day 1
Target Engagement sample			X	Day 1

 ECG/Vital signs recordings will be performed in triplicate at visit. Use the mean of the triplicate measurements.

Unless otherwise stated, if baseline data is missing no derivation will be performed and baseline will be set to missing.

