**11.3. Appendix 3: Assessment Windows**

**11.3.1. Definitions of Assessment Windows for Analyses**

No Assessment Windows will be defined for Analysis, and summaries and analyses will be based on nominal visits.

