## 11.6. Appendix 6: Derived and Transformed Data

### 11.6.1. General

Multiple Measurements at One Analysis Time Point

 
• Mean of the measurements will be calculated and used in any derivation of summary statistics but if listed, all data will be presented.
 
• If there are two values within a time window (as per Section 11.3.1) the value closest to the target day for that window will be used. If values are the same distance from the target, then the mean will be taken.
 
• Participants having both High and Low values for Normal Ranges at any post-baseline visit for safety parameters will be counted in both the High and Low categories of “Any visit post-baseline” row of related summary tables. This will also be applicable to relevant Potential Clinical Importance summary tables.
 

Study Day

 
• Calculated as the number of days from First Dose Date:                             
 
• Ref Date = Missing → Study Day = Missing
 
• Ref Date < First Dose Date → Study Day = Ref Date – First Dose Date
 
• Ref Date ≥ First Dose Date → Study Day = Ref Date – (First Dose Date) + 1
 
 
 

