## 11.10.5. Safety Tables

Safety: Tables					
No.	Population	IDSL / Example Shell	Title	Programming Notes	Deliverable [Priority]
Adverse Events (AEs)					
3.1.	Safety	AE1CP	Summary of All Adverse Events by System Organ Class and Preferred Term: Part A	ICH E3	SAC
3.2.	Safety	AE5A	Summary of All Adverse Events by Maximum Grade / Intensity by System Organ Class and Preferred Term: Part A	ICH E3	SAC
3.3.	Safety	AE5A	Summary of All Drug-Related Adverse Events by System Organ Class and Preferred Term and Maximum Intensity: Part A	ICH E3	SAC
3.4.	Safety	AE15	Summary of Common ( $\geq 10\%$ ) Non-serious Adverse Events by System Organ Class and Preferred Term (Number of Participant and Occurrences) : Part A	FDAAA, EudraCT	SAC
Serious and Other Significant Adverse Events					
3.5.	Safety	AE16	Summary of Serious Adverse Events by System Organ Class and Preferred Term (Number of Subjects and Occurrences) : Part A	FDAAA, EudraCT	SAC
3.6.	Safety	AE3	Summary of Adverse Events Leading to Permanent Discontinuation of Study Treatment or Withdrawal from Study by System Organ Class and Preferred Term /by Overall Frequency: Part A	IDSL	SAC
Laboratory: Chemistry					
3.7.	Safety	LB1	Summary of Chemistry Changes from Baseline: Part A	ICH E3	SAC

Safety: Tables					
No.	Population	IDSL / Example Shell	Title	Programming Notes	Deliverable [Priority]
3.8.	Safety	LB17	Summary of Worst Case Chemistry Results by PCI Criteria Post-Baseline Relative to Baseline: Part A	ICH E3	SAC
Laboratory: Hematology					
3.9.	Safety	LB1	Summary of Hematology Changes from Baseline: Part A	ICH E3	SAC
3.10.	Safety	LB17	Summary of Worst Case Hematology Results by PCI Criteria Post-Baseline Relative to Baseline: Part A	ICH E3	SAC
Laboratory: Urinalysis					
3.11.	Safety	LB1	Summary of Urine Concentration Changes from Baseline: Part A	ICH E3	SAC
3.12.	Safety	UR1	Summary of Worst Case Urinalysis Results (Discrete or Character Values) Post-Baseline Relative to Baseline: Part A	ICH E3	
Laboratory: Hepatobiliary (Liver)					
3.13.	Safety	LIVER1	Summary of Liver Monitoring/Stopping Event Reporting: Part A	IDSL	SAC
3.14.	Safety	LIVER10	Summary of Hepatobiliary Laboratory Abnormalities: Part A	IDSL	SAC
ECG					
3.15.	Safety	EG1	Summary of ECG Findings : Part A	IDSL	SAC
3.16.	Safety	EG10	Summary of Maximum QTc Values Post-Baseline Relative to Baseline by Category: Part A	IDSL	SAC

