3.17.	Safety	EG2	Summary of Change from Baseline in ECG Values by Visit: Part A	IDSL	SAC
3.18.	Safety	EG11	Summary of Maximum Increase in QTc Values Post-Baseline Relative to Baseline by Category: Part A	IDSL	SAC

Safety: Tables					
No.	Population	IDSL / Example Shell	Title	Programming Notes	Deliverable [Priority]
Vital Signs					
3.19.	Safety	VS1	Summary of Change from Baseline in Vital Signs: Part A	ICH E3	SAC
3.20.	Safety	VS3 / VS6 / VS7	Summary of Worst Case Vital Signs Results by PCI Criteria Post-Baseline Relative to Baseline: Part A	IDSL	SAC
Holter					
3.21.	Safety	HM1	Summary of Holter Interpretations: Part A		SAC
3.22.	Safety	HM2	Summary of Holter Abnormalities: Part A		SAC

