## 11.10.6. Safety Figures

Safety: Figures					
No.	Population	IDSL / Example Shell	Title	Programming Notes	Deliverable [Priority]
Adverse Events					
3.1.	Safety	AE10	Plot of Common ( $\geq 10\%$ ) Adverse Events and Relative Risk: Part A	IDSL	SAC
Laboratory					
3.2.	Safety	LIVER14	Scatter Plot of Maximum vs. Baseline for ALT: Part A	IDSL	SAC
3.3.	Safety	LIVER9	Scatter Plot of Maximum ALT vs. Maximum Total Bilirubin: Part A	IDSL	SAC
3.4.	Safety	SAFE_01	Individual Profile Plots for Liver Function Tests : Part A	Page by liver function test (ALT, AST, ALKP, BILI) Scheduled & Unscheduled Visits to be presented Panel by subject Lower reference line ULN, High Reference Line PCI as y-axis allows. Label reference line clearly on figure or in legend	SAC
3.5.	Safety	SAFE_02	Box Plot of Liver Function Tests by Period: Part A	Page by liver function test (ALT, AST, ALKP, BILI) Scheduled visits only	SAC

Safety: Figures					
No.	Population	IDSL / Example Shell	Title	Programming Notes	Deliverable [Priority]
3.6.	Safety	SAFE_01	Individual Profile Plots for Renal Function Tests: Part A	Page by renal function test (Blood Urea Nitrogen, Calcium, Creatinine, Gamma GT, Potassium, Sodium, Blood Glucose – fasted, Urea) Scheduled & Unscheduled Visits to be presented Panel by subject LLN and ULN to be included as y-axis allows Label reference line clearly on figure or in legend	SAC
3.7.	Safety	SAFE_02	Box Plot of Liver Function Tests by Period: Part A	Page by renal function test (Blood Urea Nitrogen, Calcium, Creatinine, Gamma GT, Potassium, Sodium, Blood Glucose – fasted, Urea) Scheduled Visits Only	SAC

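### SAP 11.5.2 bars unscheduled visits from all summary tables and figures, so eight worst-case or maximum displays of measured values can understate a participant's worst post-baseline value

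*SAP*

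**What the plan says.** - **The exclusion.** SAP 11.5.2 (Reporting Standards): "Unscheduled visits will not be included in summary tables and/or figures". The same section keeps all unscheduled visits in the listings.
- **No windows.** SAP 11.3.1 defines no assessment windows; "summaries and analyses will be based on nominal visits". An unscheduled value therefore cannot be slotted into a scheduled visit.
- **The displays.** SAP 11.10.5 plans tables such as 3.8, "Summary of Worst Case Chemistry Results by PCI Criteria Post-Baseline Relative to Baseline: Part A", and 3.18, "Summary of Maximum Increase in QTc Values Post-Baseline Relative to Baseline by Category: Part A". SAP 11.10.6 plans Figure 3.3, "Scatter Plot of Maximum ALT vs. Maximum Total Bilirubin: Part A". The programming notes for the eight displays say only ICH E3 or IDSL (the sponsor's display standards).
- **The stated exceptions.** Figures 3.4 and 3.6, the individual liver and renal profile plots, carry the note "Scheduled & Unscheduled Visits to be presented". No other display does.
- **Baseline.** SAP 5.2 takes the latest non-missing pre-dose value, "including those from unscheduled visits".
- **A neighbouring rule.** SAP 11.6.1: "Participants having both High and Low values for Normal Ranges at any post-baseline visit for safety parameters will be counted" in both categories. It extends this to the relevant tables of potential clinical importance (PCI) and does not mention unscheduled visits.

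**The concern.** A worst-case or maximum display answers one question: how extreme did this participant get? A rule that drops some post-baseline values before the extreme is taken can give the wrong answer, and only in the reassuring direction. The dropped values are also not a random subset. In this protocol, unscheduled measurements arise largely because a result was abnormal and had to be followed.

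Safety is the primary objective and the dose groups are very small, so a single category shift is visible in the percentages. There is also an asymmetry: an unscheduled value may serve as the baseline but, under 11.5.2, may not serve as the post-baseline worst value compared with it.

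**Working it through.** The plan gives no figure on this point to reproduce. The check is a count of displays, a direction argument and a bound on size.

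**1. Which displays are affected.** Ten display titles in SAP Appendix 10 contain worst case or maximum: Tables 3.2, 3.3, 3.8, 3.10, 3.12, 3.16, 3.18 and 3.20, and Figures 3.2 and 3.3. Tables 3.2 and 3.3 summarise adverse event intensity and are not visit-based, so the rule does not touch them. That leaves 10 − 2 = 8 displays of measured values. Three of these (3.8, 3.10, 3.20) are titled as PCI tables; 8 − 3 = 5 are not.

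**2. Direction.** Let S be a participant's scheduled post-baseline values and U the unscheduled ones. For a fixed baseline, max(S and U) = max(max S, max U) ≥ max S. For low limits the same holds with the minimum reversed. Omitting U leaves the participant in the same category or a milder one.

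**3. Where U comes from.** Protocol 10.3.5 asks for clinically significant laboratory abnormalities to be repeated. Appendix 6 requires repeat liver chemistries within 24 h or 24–72 h of a stopping event, then twice-weekly or weekly monitoring. Section 10 allows extra safety samples. For ECGs, post-dose readings in Part A are scheduled as single, 9.4 judges QTc withdrawal on triplicate averages, and 10.3.4 foresees further QTc readings.

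**4. In house or after discharge.** Participants stay through 48 h. An extra in-house reading entered under a nominal time point is averaged with the scheduled one (11.6.1), not dropped. After the last period, nothing is scheduled between 48 h (2 days) and follow-up at about 7 to 14 days: 7 − 2 = 5 to 14 − 2 = 12 days. A repeat in that gap has no nominal visit and falls squarely under 11.5.2.

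**5. Illustrations.** All values are assumed. The limits are from SAP 11.8, and I assume that Table 3.8 applies the liver limits and Table 3.16 the QTc categories given there.

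| Case | Scheduled | Unscheduled | Shown | All values |
|---|---|---|---|---|
| ALT, repeat after discharge | 1.8 and 1.1 × ULN | 2.4 × ULN | below 2 × ULN, no flag | flag |
| Liver event | ALT 3.2, bilirubin 1.2 × ULN | ALT 2.8, bilirubin 1.6 × ULN | ALT flag only | ALT, bilirubin and combined flags |
| QTcF | single 478 msec (H1) | triplicate mean 484 msec (H2) | H1 | H2 |

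- In the liver case the ALT flag cannot change, because the 3 × ULN trigger already exceeds the 2 × ULN limit.
- The QTcF case is the weakest. A reading of 478 msec is not above 500, so the stopping rule would prompt a confirmation only if baseline were below 478 − 60 = 418 msec. If the triplicate were entered under the nominal time point, the average would be (478 + 484)/2 = 481, or (478 + 3 × 484)/4 = 482.5 over the four tracings. Both are H2, so nothing would be lost in that example.

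**6. Size.** Protocol 5.2 plans 8 active participants per dose in Cohort 1 and 9 in Cohort 2. One shift is 1/8 = 12.5 points or 1/9 = 11.1 points; two shifts are 25.0 or 22.2 points. The number of shifts is not in the documents and may be zero.

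**The case against.** **The display shells are not in the documents and may define their own records.** They cannot be checked. However, 11.5.2 applies the sponsor's display standards only where the SAP does not state otherwise, and here it does. If the shells do include unscheduled values, the SAP contradicts its own displays and the same sentence is needed.

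**SAP 11.6.1 speaks of any post-baseline visit.** That rule settles how to count a participant with both high and low values. Even read generously, it reaches the PCI tables and leaves the other five displays uncovered.

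**The exclusion concerns visits, not readings.** This stands in part. SAP 11.5.2 also speaks of unscheduled readings when it describes listings, so an extra in-house measurement may belong to a nominal visit. This narrows the concern mainly to tests after discharge.

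**The signal is carried elsewhere.** This stands and limits the consequence.
- The dedicated PCI listings (19–20, 22, 23–26 and 29–30) would hold the values.
- Figures 3.4 and 3.6 plot liver and renal values.
- Table 3.13 reports liver events.
- Clinically significant abnormalities meet the adverse event definition in protocol Appendix 4 and so reach the adverse event tables.
- Withdrawal visits may be summarised separately (SAP 11.7.1).

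None of these corrects the eight displays. Subject-level listings are kept out of the report's main body, and no figure shows unscheduled QTc, vital-sign, haematology or urinalysis values.

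**Understatement needs a repeat that is worse than the trigger and crosses a limit.** This is true. The triggering value is often scheduled and already displayed.

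A reader might infer that safety findings are hidden, or that participants have been misclassified. The documents support neither: no value is discarded, and no affected participant can be identified from them.

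**Conclusion.** The point holds as a defect in the rule. Applied as written, SAP 11.5.2 lets eight displays of measured values omit the value that their titles promise, with error possible in one direction only. It does not hold for the adverse event intensity tables, and it is uncertain for extra readings taken in house.

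The size is 12.5 or 11.1 percentage points per participant affected, with an unknown and possibly zero number affected. This rests on three assumptions: 11.5.2 is followed literally, the repeat is recorded as an unscheduled visit, and the planned denominators apply. Given the remaining routes to the data and the absence of any formal hypothesis test, this is minor to should-fix. It is worth correcting because safety is the primary endpoint and the correction is cheap.

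**What to change.** Replace the exclusion in SAP 11.5.2 with text to this effect:

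> Unscheduled visits are excluded from by-visit summaries only. Tables 3.8, 3.10, 3.12, 3.16, 3.18 and 3.20 and Figures 3.2–3.3 use all valid post-baseline values, scheduled and unscheduled; results voided for a technical sample problem are excluded. An unscheduled value is assigned to the period of the most recent dose if taken before the next period's Day -1 assessments; from then until the next dose it is treated as pre-dose for the next period under 5.2. Values in the 11.4.1 Post-Treatment phase are included for these displays.

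The last sentence is needed because 11.4.1 ends the on-treatment phase one day after the dose. With a single dose on Day 1 that is Day 2, so even the scheduled 48 h assessment on Day 3 counts as post-treatment.

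Apply the same rule to Table 3.14 if its shell uses a worst or any-time post-baseline value. Keep the QTcF rule with QTcB fallback in 11.8.2. Footnote each display to say that unscheduled values are included.

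**Cost:** one SAP paragraph, a programming flag and the footnotes; no new data, and by-visit summaries are unchanged. The downside is that participants with more repeat tests have more chances to show an extreme, which the footnote discloses.

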### 11.5.3. Reporting Standards for Pharmacokinetic

Pharmacokinetic Concentration Data	
PC Windows Non-Linear (WNL) File	PC WNL file (CSV format) for the non compartmental analysis by Clinical Pharmacology Modelling and Simulation function will be created according to PKOne Note: Concentration values will be imputed as per GUI_51487
Descriptive Summary Statistics, Graphical Displays and Listings	Refer to IDSL PK Display Standards. Refer to IDSL Statistical Principle 6.06.1. Note: Concentration values will be imputed as per GUI_51487 for descriptive summary statistics/analysis and summarized graphical displays only.
NONMEM/Pop PK File	Not applicable.
NONMEM/PK/PD File	Not applicable
Pharmacokinetic Parameter Derivation	
PK Parameter to be Derived by Programmer	Not applicable
Pharmacokinetic Parameter Data	
Is NQ impacted PK Parameters Rule Being Followed	Yes, refer to Standards for Handling NQ Impacted PK Parameters.
Descriptive Summary Statistics, Graphical Displays and Listings	Refer to IDSL PK Display Standards. Refer to PKOne

## 11.6. Appendix 6: Derived and Transformed Data

### 11.6.1. General

Multiple Measurements at One Analysis Time Point

 
• Mean of the measurements will be calculated and used in any derivation of summary statistics but if listed, all data will be presented.
 
• If there are two values within a time window (as per Section 11.3.1) the value closest to the target day for that window will be used. If values are the same distance from the target, then the mean will be taken.
 
• Participants having both High and Low values for Normal Ranges at any post-baseline visit for safety parameters will be counted in both the High and Low categories of “Any visit post-baseline” row of related summary tables. This will also be applicable to relevant Potential Clinical Importance summary tables.
 

Study Day

 
• Calculated as the number of days from First Dose Date:                             
 
• Ref Date = Missing → Study Day = Missing
 
• Ref Date < First Dose Date → Study Day = Ref Date – First Dose Date
 
• Ref Date ≥ First Dose Date → Study Day = Ref Date – (First Dose Date) + 1
 
 
 

### 11.6.2. Study Population

Treatment Compliance

 
• Treatment compliance will be calculated based on the formula:  Treatment Compliance = Number of Actual Doses / (Planned Treatment Duration in Days * Frequency) 
 
• Planned Treatment Duration is defined as 1 day in Part A in each period
 

Extent of Exposure

 
• Number of days of exposure to study drug will be calculated based on the formula:  Duration of Exposure in Days = Treatment Stop Date – (Treatment Start Date) + 1 
 
• Participants who were randomised but did not report a treatment start date will be categorised as having zero days of exposure.
 
• The cumulative dose will be based on the formula:  Cumulative Dose = Sum of (Number of Days x Total Daily Dose) 
 
• If there are any treatment breaks during the study, exposure data will be adjusted accordingly.
 

### 11.6.3. Safety

ECG Parameters
RR Interval

 
• IF RR interval (msec) is not provided directly, then RR can be derived as:                             
 
○ If QTcF is machine read, then:                                     <math display="block">RR = \left[ \left( \frac{QT}{QTcF} \right)^3 \right] * 1000</math> 
 
 
 
• If ECGs are manually read, the RR value preceding the measurement QT interval should be a
 

**ECG Parameters**

collected value THEN do not derive.

**Corrected QT Intervals**

- When not entered directly in the eCRF, corrected QT intervals by Fridericia's (QTcF) formulas will be calculated, in msec, depending on the availability of other measurements.
- IF RR interval (msec) is provided then missing QTcF will be derived as:

$$QT_{cF} = \frac{QT}{\sqrt[3]{\frac{RR}{1000}}}$$

**Laboratory Parameters**

- If a laboratory value which is expected to have a numeric value for summary purposes, has a non-detectable level reported in the database, where the numeric value is missing, but typically a character value starting with '<x' or '>x' (or indicated as less than x or greater than x in the comment field) is present, the number of significant digits in the observed values will be used to determine how much to add or subtract in order to impute the corresponding numeric value.
  - Example 1: 2 Significant Digits = '< x' becomes x - 0.01
  - Example 2: 1 Significant Digit = '> x' becomes x + 0.1
  - Example 3: 0 Significant Digits = '< x' becomes x - 1

